
13.5.5. Virology

Genotype	
Amino Acid Changes	

 A mutation is considered present whenever the encoded amino acid residue differs from the amino acid that would have been encoded by the wild-type (e.g., HXB2, NL43) comparator gene; e.g., Q148K. If the encoded amino acid is seen as a mixture of wild-type and mutant amino acid, e.g., Q148Q/K, the mutated amino acid is considered present at the codon of interest. If the encoded amino acid is seen as a mixture of two or more amino acids, which may or may not include wild type, e.g., Q184K/H or Q184K/H/Q, etc., for the purposes of calculating the number of mutated amino acids, only one mutation is considered to be present at the codon of interest. 	
Representation of Amino Acid Changes	
Mutations	Amino Acid Change
T69S	Single mutation from amino acid 'T' (vendor reference) to 'S' (sample) at codon '69'
Q148H/K/R	Mixture of amino acid mutations 'H', 'K' and 'R' (sample) from amino acid 'Q' (vendor reference) at codon '148'
_69_1T	First insertion of amino acid 'T' (sample) at codon '69'
_69_2S	Second insertion of amino acid 'S' (sample) at codon '69'
_69_3S/A	Third insertion of a mixture of amino acids 'S' and 'A' (sample) at codon '69'
L74L/-	Mixture of amino acid 'L' (sample) and a deletion at codon '74'
V75-	Single deletion of amino acid (sample) at codon '75'
Resistance Associated mutations	
Known INI mutations associated with the development of resistance to Integrase Strand Transfer Inhibitors:	
Amino Acids in HIV Integrase for Analysis	H51Y, T66A/I/K , L68V/I, L74I/M, E92Q/V/G , Q95K, T97A, G118R , F121Y , E138A/D/K/T, G140A/C/R/S , Y143C/H/R/K/S/G/A , P145S, Q146P, S147G , Q148H/K/R/N , V151/I/L/A, S153F/Y, N155H/S/T , E157Q, G163R/K, G193E, S230R, R263K

 Draft listing; may be modified in case of additional substantive data availability. Based on the IAS-USA list of mutations associated with resistance to Bictegravir, Cabotegravir, Dolutegravir, Elvitegravir, or Raltegravir (IAS-USA 2019 resistance mutations update volume 27 issue 3, 2019): T66A/I/K, L74M, E92Q/G, T97A, G118R, F121Y, E138A/K/T, G140A/C/R/S, Y143C/H/R, S147G, Q148H/K/R, S153F/Y, N155H, R263K) and observed mutations during in vitro passage of DTG or seen in a previous DTG study in INI-experienced subjects (study ING112574): H51Y, L74I, L68V/I, E92V, Q95K, E138D, Y143K/S/G/A, P145S, Q146P, V151I/L/A, N155S/T, E157Q, G163R/K, G193E, S230R. Major USA-IAS mutations associated with resistance to INSTI are bolded. Major resistance mutations to other classes (i.e., NRTI, NNRTI, PI) as defined by the International Antiviral Society-USA (IAS-USA). The most up to date IAS-USA guidelines available at the time of DBF will be used in the analysis [Wensing, 2019]. 	
Class	Mutations
NRTIs	M41L, A62V, K65R/E/N, D67N, 69 insert, K70E/R, L74V, V75I, F77L, Y115F, F116Y, Q151M, M184V/I, L210W, T215Y/F, K219Q/E
NNRTIs	L100I, K101E/P, K103N/S, V106A/M, V108I, E138/A/G/K/Q/R, V179L, Y181C/I/V, Y188C/L/H, G190S/A, H221Y, P225H, F227C, M230I/L

Genotype	
PIs	D30N, V32I, M46I/L, I47A/V, G48V, I50V/L, I54V/M/L, Q58E, T74P, L76V, V82A/T/F/L/S, N83D, I84V, N88S, L90M

 Draft listing; may be modified in case of additional substantive data availability. 	

13.5.6. Other Assessments

Study Visit Length

 Lead Time = Actual Start Time of Appointment – Arrival Time Process Time = Actual End Time of Appointment – Actual Start Time of Appointment Total Time = Actual End Time of Appointment – Arrival Time

13.6. Appendix 6: Reporting Standards for Missing Data

13.6.1. Premature Withdrawals

Element	Reporting Detail
General	
 Withdrawn participants were not replaced in the study. All available data from participants who were withdrawn from the study will be listed and all available planned data will be included in summary tables and figures, unless otherwise specified. Withdrawal visits will be slotted according to Appendix 2: Assessment Windows (excluding PK data)

13.6.2. Handling of Missing Data

Element	Reporting Detail
General	
 Missing data occurs when any requested data is not provided, leading to blank fields on the collection instrument: 
 These data will be indicated by the use of a “blank” in participant listing displays. Unless all data for a specific visit are missing in which case the data is excluded from the table. Answers such as “Not applicable” and “Not evaluable” are not considered to be missing data and should be displayed as such.
Outliers	
 Any participants excluded from the summaries and/or statistical analyses will be documented along with the reason for exclusion in the clinical study report.

13.6.2.1. Handling of Missing and Partial Dates

Element	Reporting Detail		
General	
 Partial dates will be displayed as captured in participant listing displays. Where necessary, display macros may impute dates as temporary variables for sorting data in listings only. In addition, partial dates may be imputed for ‘slotting’ data to study phases or for specific analysis purposes as outlined below. Imputed partial dates will not be used to derive study day, time to onset or duration (e.g., time to onset or duration of adverse events), or elapsed time variables (e.g., time since diagnosis). In addition, imputed dates are not used for deriving the last contact date in overall survival analysis dataset. 		
Adverse Events	
 Imputations in the adverse events dataset are used for slotting events to the appropriate study time periods and for sorting in data listings. Partial dates for AEs recorded in the CRF will be imputed using the following conventions: 
 
 Missing start day	 
 If study treatment start date is missing (i.e. participant did not start study treatment), then set start date = 1st of month. Else if study treatment start date is not missing: 
 If month and year of start date = month and year of study treatment start date, then 	
 
 	Missing start day	
 If study treatment start date is missing (i.e. participant did not start study treatment), then set start date = 1st of month. Else if study treatment start date is not missing: 
 If month and year of start date = month and year of study treatment start date, then
Missing start day	
 If study treatment start date is missing (i.e. participant did not start study treatment), then set start date = 1st of month. Else if study treatment start date is not missing: 
 If month and year of start date = month and year of study treatment start date, then 		

Element	Reporting Detail					
		
 ▪ If stop date contains a full date and stop date is earlier than study treatment start date, then set start date= 1st of month. ▪ Else set start date = study treatment start date. • Else 
 ○ For Non-ISR AEs: set start date = 1st of month ○ For ISR AEs: if oral bridging taken during the month and year, set start date = min(last day of the month, day of AE stop date if available, day of study treatment discontinuation if occurring during the month and year); else set start date = 1st of month. 				
	Missing start day and month	
 • If study treatment start date is missing (i.e. participant did not start study treatment), then set start date = January 1. • Else if study treatment start date is not missing: 
 ○ If year of start date = year of study treatment start date, then 
 ▪ If stop date contains a full date and stop date is earlier than study treatment start date, then set start date = January 1. ▪ Else set start date = study treatment start date. ○ Else set start date = January 1. 				
	Missing stop day	Last day of the month will be used.				
	Missing stop day and month	No Imputation				
	Completely missing start/end date	No imputation				
Non-ART Medications (including Oral Bridging CAB + RPV)		
 • Completely missing start or end dates will remain missing, with no imputation applied. • Partial dates for any concomitant medications recorded in the CRF will be imputed using the following convention: 
  
 Missing start day	 
 • If study treatment start date is missing (i.e. participant did not start study treatment), then set start date = 1st of month. • Else if study treatment start date is not missing: 
 ○ If month and year of start date = month and year of study treatment start date, then 
 ▪ If stop date contains a full date and stop date is earlier than study treatment start date, then set start date= 1st of month. ▪ Else set start date = study treatment start date. ○ Else set start date = 1st of month. 	
 
 Missing start day and month	 
 • If study treatment start date is missing (i.e. participant did not start study treatment), then set start date = January 1. • Else if study treatment start date is not missing: 
 ○ If year of start date = year of study treatment start date, then 
 ▪ If stop date contains a full date and stop date is earlier than study treatment start date, then set start date = January 1. ▪ Else set start date = study treatment start date. • Else set start date = January 1. 	
  
 	Missing start day	
 • If study treatment start date is missing (i.e. participant did not start study treatment), then set start date = 1st of month. • Else if study treatment start date is not missing: 
 ○ If month and year of start date = month and year of study treatment start date, then 
 ▪ If stop date contains a full date and stop date is earlier than study treatment start date, then set start date= 1st of month. ▪ Else set start date = study treatment start date. ○ Else set start date = 1st of month. 	Missing start day and month	
 • If study treatment start date is missing (i.e. participant did not start study treatment), then set start date = January 1. • Else if study treatment start date is not missing: 
 ○ If year of start date = year of study treatment start date, then 
 ▪ If stop date contains a full date and stop date is earlier than study treatment start date, then set start date = January 1. ▪ Else set start date = study treatment start date. • Else set start date = January 1.
Missing start day	
 • If study treatment start date is missing (i.e. participant did not start study treatment), then set start date = 1st of month. • Else if study treatment start date is not missing: 
 ○ If month and year of start date = month and year of study treatment start date, then 
 ▪ If stop date contains a full date and stop date is earlier than study treatment start date, then set start date= 1st of month. ▪ Else set start date = study treatment start date. ○ Else set start date = 1st of month. 					
Missing start day and month	
 • If study treatment start date is missing (i.e. participant did not start study treatment), then set start date = January 1. • Else if study treatment start date is not missing: 
 ○ If year of start date = year of study treatment start date, then 
 ▪ If stop date contains a full date and stop date is earlier than study treatment start date, then set start date = January 1. ▪ Else set start date = study treatment start date. • Else set start date = January 1. 					

Element	Reporting Detail						
	
 
 Missing end day	A '28/29/30/31' will be used for the day (dependent on the month and year)	
 
 Missing end day and month	A '31' will be used for the day and 'Dec' will be used for the month.	
 
 Completely missing start/end date	No imputation	
 
 
 The recorded partial date will be displayed in listings. 	Missing end day	A '28/29/30/31' will be used for the day (dependent on the month and year)	Missing end day and month	A '31' will be used for the day and 'Dec' will be used for the month.	Completely missing start/end date	No imputation
Missing end day	A '28/29/30/31' will be used for the day (dependent on the month and year)						
Missing end day and month	A '31' will be used for the day and 'Dec' will be used for the month.						
Completely missing start/end date	No imputation						
ART Medications	
 Partial dates recorded in the eCRF will be imputed using the following convention: 
 If the partial date is a start date, a '01' will be used for the day and 'Jan' will be used for the month. If the partial date is a stop date, a '28/29/30/31' will be used for the day (dependent on the month and year) and 'Dec' will be used for the month. If medications recorded in the PRIOR ART form of the eCRF, then the earlier date of the imputed and the day prior to the maintenance phase treatment start date will be used, i.e. min (imputed stop date, Intervention phase treatment start date - 1). For medications with completely missing start date, they will be considered started prior to the Intervention phase treatment start date. For medications with completely missing stop date, they will be considered ongoing unless recorded in the PRIOR ART form of the eCRF. For ART booster medications, the start and stop dates are not recorded in the database (i.e. missing), the dates will be imputed to be the same as the dates of their parent medications. The recorded partial or missing date will be displayed in listings. 						

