6.5.3. IM Dosing

Participants receiving CAB LA and/or RPV LA are anticipated to be at risk for development of virologic resistance if antiretroviral therapy is interrupted. The time period during which participants are at risk for development of virologic resistance may be determined by the period between when drug levels fall below therapeutic values and when they fall below levels which exert selective pressure on HIV. This time period will vary by ART agent and is dependent upon effective concentration, inhibitory concentration, and half-life. Plasma concentrations of both LA drugs may be measurable for more than one year following IM injections. Any interruption in IM dosing should be discussed with the Medical Monitor. Investigators should ensure that the participant initiates alternative highly active ART to minimize the risk of developing resistance as concentrations of and RPV decline over time.

CAB LA + RPV LA dosing for participants transitioning from oral CAB + RPV is as follows:

All injections should be planned as single injections per drug.

Target Date

The patient's 'target date' is determined by their first injection date and ideally is the same date for every injection. For example, if the1st dose (Month 1) is January 15th, then dose 2 (Month 2) will be February 15th, and dose 3 (Month 4) will be April 15th, etc.

Since the first injection visit (Month 1) will determine the future injection visit schedule for participants and ideally be between the 1st and 28th day of the month. Planning for the first injection visit date (within allowed visit windows) should take into consideration the availability of the participants to adhere to future visit windows (planned vacations, business trips, *etc.*).

Treatment Injections- Months 1 and 2 -one month apart

Participants will take the last dose of their oral (CAB 30 mg + RPV 25mg) and receive the first CAB LA (600mg) + RPV LA (900mg) injections (within 2 hours of the final oral dose of CAB + RPV).

The second dose (CAB LA 600mg + RPV LA 900mg) will be administered one month later (preferable on the same target date as Dose 1). The dosing window for Dose 2 allows administration -7days of the proposed visit date but not later.

Treatment Injections- Months 4- Q2M dosing

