13.5. Appendix 5: Derived and Transformed Data

13.5.1. General

Multiple Measurements at One Analysis Time Point
 
 • If there are two values within a time window (as per Section 13.2.1) the value closest to the target day for that window will be used. If values are the same distance from the target, then the mean (geometric mean for HIV-1 RNA, arithmetic mean for all other measurement) will be taken. • Assessments not chosen for use in summary statistics by this algorithm will still appear in the associated listings. • All applicable valid assessments, irrespective of proximity to the target study day, will be used when categorizing values across visits, such as ‘maximum grade during the intervention phase’ or ‘at any time post-baseline’, and for any algorithm that has specific rules for which observation to use (e.g. snapshot algorithm, LOCF or CVF identification). • Participants having both High and Low values for Normal Ranges at any post-baseline visit for safety parameters will be counted in both the High and Low categories of “Any visit post-baseline” row of related summary tables. This will also be applicable to relevant Potential Clinical Importance summary tables.

Treatment Start Date
 
 • Intervention Phase Treatment Start Date = Earliest date of CAB + RPV oral lead-in entered in the IP exposure eCRF form

Nominal Month 14 Visit Date
 
 • For participants who received Month 14 injection, the nominal Month 14 visit date is defined by the Month 14 injection date. • Otherwise, nominal Month 14 visit date is defined by the date of latest Month 14 assessment. • For participants who continued into Extension Phase but missed the Month 14 visit, the nominal Month 14 visit date is defined by the last contact date prior to the date of the first nominal extension phase visit (i.e. Month 16, Month 18, etc.).

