13.12.8. Safety Figures

Safety: Figures					
No.	Population	GSK Standard / Example Shell	Title	Programming Notes	Deliverable
Adverse Events					
3.1.	Safety	201584/primary_07/F3.14	Plot of Incidence of Study Drug Injection Site Reaction Adverse Events by Implementation Arm and Visit (Overall and Common) – CAB and/or RPV	Sort by CAB+RPV, CAB, then RPV ISR onset assigned to most recent IM injection Visit	M12, EOS
CCI					
Laboratory					
3.3.	Safety	LIVER14	Scatter Plot of Maximum vs. Baseline for ALT	GSK Statistical Display Standard	M12, EOS
3.4.	Safety	LIVER9	Scatter Plot of Maximum Total Bilirubin vs Maximum ALT – eDISH Plot	GSK Statistical Display Standard	M12, EOS

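### Outside oral-bridging months, an injection-site reaction with a missing start day is dated without reference to any injection, so a Dose 1 reaction can enter the oral lead-in tables

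*SAP*

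**What the plan says.** SAP 13.6.2.1 gives the rules for adverse events with an incomplete start date. On the use of the imputed date it says: "Imputations in the adverse events dataset are used for slotting events to the appropriate study time periods and for sorting in data listings". SAP 13.3.2 also applies it to treatment state. The same section bars imputed dates from deriving study day, time to onset or duration.

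For an ISR with a missing start day there are three branches:

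- **Month in which study treatment began:** "Else set start date = study treatment start date", unless a full stop date falls earlier. SAP 13.5.1 defines that date: "Intervention Phase Treatment Start Date = Earliest date of CAB + RPV oral lead-in entered in the IP exposure eCRF form".
- **Other month with oral bridging:** "For ISR AEs: if oral bridging taken during the month and year, set start date = min(last day of the month", the AE stop day if available, or the "day of study treatment discontinuation if occurring during the month and year); else set start date = 1st of month".
- **Any other month:** the closing words of that same rule, "else set start date = 1st of month".

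The separate rule for a missing day and month has no ISR provision.

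SAP Table 12 places an AE in the oral lead-in if it starts on or after treatment start and before the first injection. Its footnote keeps out only AEs whose start date is completely missing. Tables 3.13 and 3.20 report lead-in AEs and drug-related lead-in AEs. The programming note for Figure 3.1 reads: "ISR onset assigned to most recent IM injection Visit".

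**The concern.** A reaction to a study injection cannot begin before the injection. The SAP gives ISRs their own rule for bridging months but leaves the ordinary month on the generic convention, and no branch looks at an injection date.

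Two outputs are exposed. The first is the set of oral lead-in tables. Neither 3.13 nor 3.20 excludes ISRs, although Tables 3.12 and 3.22 do so for their own summaries. SAP 13.5.4 also counts an ISR with missing causality as drug-related. The lead-in tables could therefore show drug-related injection-site reactions in a period with no injections. The second is Figure 3.1, where the dose to which a reaction is credited depends on its onset date.

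**Working it through.** The documents give no figure for this rule, so there is nothing to reproduce. The check applies the rules to dates.

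**Inputs.** Protocol 6.5.3 says the first injection should "ideally be between the 1st and 28th day of the month", with later injections ideally on the same date. Injections fall at Months 1, 2, 4, 6, 8, 10 and 12. Assumptions: target days uniform over 1 to 28, a lead-in of 28 or 30 days, injections on the target date and no oral bridging.

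**Share of target days.** If the recorded month contains the causal injection on day d, the imputed 1st is strictly earlier for d = 2 to 28. That is 27/28 = 96.4% of target days. The mean gap when it is earlier is (1 + 2 + ... + 27)/27 = 14 days.

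**Dose 1, worked example.** Take the protocol's own illustration, Dose 1 on 15 January, with a 30-day lead-in starting 16 December. An ISR recorded as January with no day is dated 1 January. Since 16 December ≤ 1 January < 15 January, it is a lead-in event under Table 12. The footnote does not remove it, because the date is partial and not completely missing.

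**Later doses, Figure 3.1 note.** In the same example Dose 2 is 15 February and Dose 3 is 15 April. A Dose 3 ISR recorded as April with no day is dated 1 April. The most recent injection on that date is Dose 2.

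**Allowing for a delay to onset.** With onset uniform over 0 to L days after the injection, the share of partial-dated ISRs not matched to their own injection under the Figure 3.1 note is:

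- L = 0: 96.4%
- L = 1: 96.3%
- L = 3: 95.7%
- L = 7: 90.6%

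For Dose 1 the same percentages fall in the oral lead-in. The share drops as L grows because some reactions begin in the following month, where the 1st comes after the injection and is attributed correctly.

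**Midpoint visit windows (SAP 13.2.1, Table 1).** Misplacement is 0% at Months 1, 4, 6, 8, 10 and 12. From Month 4 on, the windows open about 30 days before the target and the 1st is at most 27 days before it; the Month 1 window opens at Study Day 2. In the example, the Month 4 window opens on 17 March (15 February + floor(59/2) + 1 days, in a 28-day February), so 1 April stays in Month 4. Month 2 differs because Doses 1 and 2 are one month apart: 39 to 45% are misplaced. Over all doses the figure is 5.5 to 6.4%.

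**Treatment-start-month branch.** With a first injection on day d ≤ 28 and a lead-in of at least 28 days, treatment starts on day d − 28 ≤ 0 of the injection month, that is, in the month before. The branch therefore needs a shorter lead-in or a first injection after the 28th. When it does apply, the imputed date is the first lead-in dose, which is also before any injection.

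**The case against.** The strongest objection is that most of the apparent damage is not established.

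- A reader might infer that later ISRs are credited to the previous injection throughout the by-visit AE outputs. The documents do not support that. The most-recent-injection rule is a note to Figure 3.1 alone; SAP 13.2.1 assigns AEs to midpoint windows, which hold up except at Month 2. This stands.
- Even for Figure 3.1, nothing says that imputed dates are used. SAP 13.6.2.1 limits what they may feed, the figure's shell belongs to another study and is not available, and parts of the safety section and display list are redacted. The Figure 3.1 effect is therefore conditional. This stands too.
- A reader might infer that 96% of all partial-dated ISRs are wrong. The 27/28 is a share of target days, given that the onset month contains the causal injection. From Dose 3 alternate months normally have no injection, and there the 1st is attributed correctly.
- Missing start days may be rare. ISRs are assessed at every dosing visit, before and after the injection (Protocol 8.4.1 and Table 1), and have their own eCRF form.

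None of this removes the Dose 1 result. That follows from the visible text of 13.6.2.1 and Table 12 alone, and redacted ISR text elsewhere does not alter the stated rule.

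**Conclusion.** The rule is wrong as written, and the matter is minor. Outside oral-bridging months it dates an ISR without regard to any injection. A Dose 1 ISR recorded with only the month and year of the injection is placed in the oral lead-in for 27 of 28 target days, and so enters Table 3.13, and Table 3.20 if drug-related, as an event that could not have happened then. Misattribution of later doses is confined to Figure 3.1, if that figure uses imputed dates, and to Month 2 under the visit windows.

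Total ISR incidence and maximum grades over the treatment period are unaffected. The percentages rest on target days spread evenly over 1 to 28, injections given on target and no bridging. The documents give no count of partial-dated ISRs, so the number of events affected cannot be stated and could be very small.

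**What to change.** For ISR AEs, amend SAP 13.6.2.1 as follows:

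1. If the start day is missing and an injection was given in that month, set the start date to the latest injection date in that month that is not after the AE stop date.
2. If no injection qualifies, use the 1st of the month.
3. In every branch (treatment-start month, missing day and month, default), never impute an ISR before the first injection date.
4. State that the oral-bridging branch applies only when no injection was given in that month.

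For reactions that begin in the month of their injection, the imputed date is then the injection date, so they leave the lead-in tables and match their own dose under the Figure 3.1 note. It would help to state in that note whether imputed dates are used.

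The cost is a few lines of SAP text and code, with no new data. There is one small downside. A Dose 1 ISR that starts early in the next month, before Dose 2, may be moved to Dose 2 if no stop date is available; the present rule attributes that case correctly.
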